1. SCHEDULE OF ASSESSMENTS

VISIT/CYCLE	SCREENING PHASE ^a	TREATMENT PHASE				FOLLOW UP PHASE	
		CYCLE #1	CYCLE #2	PRE-OP/ SAFETY VISIT	SURGERY	POST-OP FOLLOW-UP	1-YEAR FOLLOW-UP
Scheduling window (days)	-28 to -1	1	29(± 7)	57 (± 14)		30 post-op (± 14)	365 post-op (± 30)
Informed Consent	X						
Eligibility Criteria	X						
Medical History	X						X
Physical Examination	X	X		X			X
Vital Signs	X	X	X	X		X	X
URS/Tumor Mapping	X				X		X ^b
Nephroureterectomy					X		
Surgical Specimen Assessment/Tumor Mapping		X			X		
Ophthalmic Assessment	X		X			X ^d	
Safety Laboratories ^c	X	X	X	X		X	X
Urinalysis	X	X	X	X		X	
Pregnancy Test	X	X	X	X		X	
12-lead ECG	X			X			
Echocardiogram	X						
AE Assessment	X	X	X	X		X	
Concomitant Meds	X	X	X	X	X	X	
EORTC QLQ-C30 QOL Questionnaire		X		X		X	
Drug Dispensing		X	X				
Drug Accountability			X				
Blood for Correlatives	X			X		X	
Urine for Correlatives	X			X		X	
Tissue for Correlatives	X				X		

Abbreviations

- a. Baseline/screening assessments that are conducted within 3 days prior to first treatment can be used to satisfy the Day 1 requirements. Every effort must be made to follow the schedule outlined.
- b. CT scan and cystoscopy (+/-URS)
- c. Blood draw (phosphate level testing only) on Day 14 (+/-7 days)
- d. as per physician discretion

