5. TREATMENTS

5.1. Treatments Administered

Patients will receive infigratinib 125 mg orally every day for a total of 2 cycles. Each cycle will consist in 28 days, with a schedule of 3 weeks on, 1 week off. Surgery will be performed during weeks 8-9 (week 8 being the off-week of 2nd cycle), and patients will have taken last dose of Infigratinib at least 48 hours prior to surgery.

If patients are not able to tolerate the study drug, every effort will be made to schedule the surgery as soon as possible after the patient has recovered and/or the investigator determines it is the best course of action for the patient.

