Gra de 3 ($> 2.0 - 5.0 \times \text{ULN}$)	
 • Hold dose of infigratinib until resolved to CTCAE Grade ≤ 2 • $\downarrow 1$ dose level of infigratinib

Worst Toxicity CTCAE (v5.0) Grade (Unless Otherwise Specified)	Recommended Dose Modifications any Time During a Cycle of Therapy
Gra de 4 ($> 5.0 \times \text{ULN}$)	
 • If not resolved within ≤ 14 days, discontinue subject from study drug 
For recurrent Grade 3 a symptomatic lipase or a mylase elevation despite dose reduction, drug should be held and continuation of therapy should be discussed with the medical monitor following resolution to \leq Grade 2.
 
For any Grade 4 a symptomatic lipase or a mylase elevation, drug should be held and continuation of therapy should be discussed with the medical monitor following resolution to \leq Grade 2.

Hyperphosphatemia	

Serum phosphorus $> 5.5 - 7.0 \text{ mg/dL}$
 
Serum phosphorus $> 7.0 \text{ mg/dL}$ for more than 7 days despite maximal phosphate-lowering therapy
 
Or, single serum phosphorus $> 9.0 \text{ mg/dL}$ regardless of duration or dose of phosphate lowering therapy
 
(Optimize/maximize dose and schedule of phosphate lowering therapy in accordance with package insert, country or institutional guidelines)
	
Maintain dose level of infigritinib and optimize phosphate lowering therapy as clinically indicated
 
 • Hold infigritinib dose until resolved to serum phosphorus $\leq 5.5 \text{ mg/dL}$. • Restart infigritinib at the same dose level with maximal phosphate binder dosing if the subject did not receive maximal phosphate binder dosing for serum phosphorus $> 7.0 \text{ mg/dL}$ for > 7 days. • Reduce one dose level of infigritinib if the subject had received maximal phosphate lowering therapy for serum phosphorus $> 7.0 \text{ mg/dL}$ for > 7 days or if subject had a one-time serum phosphorus of $> 9.0 \text{ mg/dL}$. Restart infigritinib with maximal phosphate binder dosing. 
It is recommended that phosphate binder dosing continues during infigritinib dose interruptions for hyperphosphatemia and that serum phosphorus values be monitored frequently, e.g., every 2-3 days.
 
Phosphate binder dosing should be held during the week off infigritinib therapy each cycle (Days 22-28) unless serum phosphorus is not normalized and during infigritinib dose interruptions for non-hyperphosphatemia AEs.

Hypercalcemia	

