5.4. Supportive Care Guidelines

5.4.1. Infigratinib Group

Any palliative and supportive care for disease related symptoms, including any medication or therapy for a concurrent medical condition are permitted, except if specifically prohibited below.

Hematopoietic Growth Factors

Hematopoietic growth factors (e.g., erythropoietin [EPO], granulocyte colony -stimulating factor (G-CSF), granulocyte-macrophage colony-stimulating factor [GM-CSF]), and blood transfusions <2 weeks prior to enrollment are not to be administered prophylactically or to be used to meet eligibility criteria. However, these drugs may be administered as per the label of these agents or as dictated by local practice or guidelines established by the American Society of Clinical Oncology (ASCO), ESMO, or other appropriate regional societies.

Management of Hyperphosphatemia

Hyperphosphatemia is a recognized on-target effect of potent and selective inhibitors of the FGFR pathway. While on infigratinib, subjects should avoid foods that are especially high in phosphate and, if possible, should restrict dietary phosphate to 600 – 800 mg/day. High-phosphate foods include dairy products; meats, nuts, and other high-protein foods; processed foods; and dark colas. Prophylactic phosphate binders, started in the evening of first dose of study drug, should be considered (e.g., sevelamer 800 mg three times a day with meals). Subjects who have experienced hyperphosphatemia should take a phosphate binder such as sevelamer, sacroferric oxyhydroxide, lanthanum carbonate, ferric citrate, etc. within 30 minutes of a meal on the day while taking infigratinib. Once the subject has had hyperphosphatemia, the subject should remain on a low phosphate diet, if possible, and take phosphate binder on the days infigratinib is taken, even if the serum phosphorus is normalized. The dose and schedule for phosphate lowering therapy should be in accordance with the package insert, country, or

institutional practice. For patient with GFR 30-49, phosphate binders will be started with first dosing and phosphate levels will be followed every 3 -4 days for the first week of treatment and then phosphate-binder dosage and serum phosphate level monitoring modified depending on serum phosphate levels. An example of a phosphate lowering regimen to manage hyperphosphatemia is provided for consideration below:

- Start sevelamer 800 mg three times a day with meals
- For serum phosphorus >5.5 – 7.0 mg/dL

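### For eGFR ≥50, footnote c read in study days leaves no required phosphate test on Days 30–49, so neither hyperphosphatemia hold limb has a guaranteed input during Cycle 2 dosing

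*Combined protocol and SAP*

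**What the plan says.** Section 5.1 gives two 28-day cycles of daily infigratinib "with a schedule of 3 weeks on, 1 week off". Counted from Day 1, dosing falls on Days 1–21 and 29–49.

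The hyperphosphatemia row of Table 2 (section 5.2.5.1) has two hold limbs. The sustained limb applies when serum phosphorus is above 7.0 mg/dL "for more than 7 days despite maximal phosphate-lowering therapy". The single-value limb applies to one reading above 9.0 mg/dL, "regardless of duration or dose of phosphate lowering therapy". Both can lead to a one-level dose reduction.

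Phosphate belongs to the safety chemistry panel (section 8.2.3, Table 6). Section 1 places that panel, during and just after treatment, at Day 1, Day 29 (±7) and Day 57 (±14). Footnote c adds "Blood draw (phosphate level testing only) on Day 14 (+/-7 days"). It does not say in which cycle.

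Three other provisions bear on repeat testing:
- Table 2 recommends that binders continue during interruptions for hyperphosphatemia and that "serum phosphorus values be monitored frequently, e.g., every 2-3 days".
- The example binder regimen in section 5.4.1 has a step for values above 7.0 and up to 9.0 mg/dL, with no date for the next test.
- For GFR 30–49 only, section 5.4.1 sets draws every 3 to 4 days "for the first week of treatment and then phosphate-binder dosage and serum phosphate level monitoring modified" according to the serum level.

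**The concern.** A hold rule protects patients only if results reach it while they are taking the drug. Hyperphosphatemia is an on-target effect of this drug class (section 5.4.1). It was the most common adverse event in phase 1, at 65.4% (section 2.4.2). In rats and dogs, raised phosphorus was associated with only partly reversible mineralization, including in the kidney (section 2.3).

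If the required draws fall after dose-free weeks, the rule works only when someone orders an extra test or when a visit happens to fall at a useful point in its window. What is at stake is patient safety, chiefly in Cycle 2. The hyperphosphatemia row contains no instruction to discontinue, so this point makes no claim about the primary endpoint.

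**Working it through.** The plan gives no figure of its own to reproduce. The check sets each required phosphate draw against the dosing days, for eGFR ≥50.

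**Inputs.** Dosing Days 1–21 and 29–49, so 21 + 21 = 42 days (section 5.1). Visit days and windows from section 1. Day 1 tests precede the first dose (section 7.3).

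| Draw | Nominal day | Window | Position against dosing |
|---|---|---|---|
| Cycle 1 visit | 1 | – | Before the first dose |
| Footnote c | 14 | 7–21 | On drug throughout |
| Cycle 2 visit | 29 | 22–36 | Nominal day follows 7 dose-free days; Days 22–28 dose-free |
| Pre-op visit | 57 | 43–71 | 57 − 49 = 8 days after the last dose; Days 43–49 on drug |

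**Study-day reading of footnote c.** One nominal draw (Day 14) reflects current exposure, in 42 dosing days. Draws required on Days 30–49: 0. The windows permit Days 30–36 and Days 43–49. The Cycle 2 visit also carries a "Drug Dispensing" entry, so a draw on Days 30–36 is an on-drug value only if Cycle 2 dosing began before the visit at which its supply is handed out.

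**Per-cycle reading.** Draws on Day 14 and Day 28 + 14 = 42 (window 35–49): two in 42 dosing days, and the Cycle 2 gap closes.

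**Which reading?** The section 1 columns count study days (1, 29, 57), which favours the first. Table 2 numbers its off week by cycle, "each cycle (Days 22-28) unless serum phosphorus is not normalized", which makes the second possible. The text does not settle it.

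**Sustained limb.** More than 7 days means at least 8. Suppose therapy becomes maximal on the day of the draw, d:
- Nominal Day 14: 14 + 8 = 22, off drug. Only 21 − 14 = 7 dosing days remain.
- Nominal Day 42: 42 + 8 = 50, off drug.
- An on-drug repeat needs d + 8 ≤ 21, so d ≤ 13. That covers Days 7–13, which is 7 of the 15 permitted days; Days 14–21 (8 of 15) do not qualify. On the per-cycle reading, Days 35–41 lead to Days 43–49.

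**Time to the next scheduled draw.** 29 − 14 = 15 days; on the per-cycle reading also 57 − 42 = 15 days. Each gap contains a full off week. A normal value on Day 29 therefore cannot show whether the level had stayed above 7.0 mg/dL past the seventh day.

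**The case against.** The strongest reply is that at nominal timing the missing recheck loses no hold. That stands. A patient put on maximal therapy on Day 14 or 42 cannot meet the sustained limb until dosing has already stopped. A reader might infer from the 15-day gap that patients would be dosed through a hold that was due; at nominal timing the arithmetic does not support this.

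Other stronger readings also fail:
- **That no on-drug test is possible in Cycle 2, or that no required draw can ever serve the sustained limb.** The pre-op draw is required and its window reaches Days 43–49. The fault is that its timing is not guaranteed.
- **That the gap covers everyone.** GFR 30–49 has fixed early draws and then monitoring guided by the level.
- **That the phase 1 rate of 28.8% counts the patients affected.** That figure is hyperphosphatemia which was detected and led to dose adjustment or interruption (section 2.4.2). The documents give no rate of undetected sustained elevation.

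On the recommended interval of 2–3 days, the mention of interruptions sits in the first clause of the sentence, so the second clause could be read more widely. The narrower reading is more natural, because the sentence belongs to the hold row and a single value of 7.0–9.0 mg/dL triggers no hold. Either way it is a recommendation with an example interval.

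Real safeguards exist: prophylactic binders to be considered, continued binders on dosing days after any episode, adverse event follow-up at each visit (section 8.2.1.5) and extra tests at the investigator's discretion (section 8.2.3). A careful investigator would probably recheck. None of these sets a date. By contrast, Table 2 does require creatinine at least weekly when a Grade 2 or higher rise accompanies hyperphosphatemia.

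**Conclusion.** The point holds for eGFR ≥50.

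**Main point.** It depends on the study-day reading. There is then one nominal on-drug draw in 42 dosing days and none required on Days 30–49. Even the single-value limb above 9.0 mg/dL has no required test during Cycle 2 dosing after Day 29. If the footnote was meant per cycle, the gap is one of wording only.

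**Secondary point.** It holds on either reading but is smaller. No recheck interval is required after an on-drug value above 7.0 and up to 9.0 mg/dL. Three situations therefore depend on discretionary tests or on where a visit falls in its window: the decision whether to reduce the Cycle 2 dose, patients drawn early in the window, and patients already on maximal therapy.

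The counts assume dosing on the nominal days without interruption. The number of patients affected cannot be estimated from the documents. This is a cheap patient-safety improvement.

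**What to change.** 1. Reword footnote c as a phosphate-only draw on Day 14 of each cycle, that is study Days 14 and 42, each ±7 days.
2. Add to Table 2 and section 5.4.1: any on-drug value above 7.0 mg/dL requires maximal phosphate-lowering therapy, a repeat within 7 days, and a further repeat once more than 7 days of maximal therapy have passed and before Cycle 2 dosing resumes. The clinical team sets the exact days.

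From a nominal draw, the first repeat falls by Day 21 or Day 49, still on drug, so it also serves the limb above 9.0 mg/dL. In Cycle 1 the second repeat can be taken from Day 22, and a Cycle 2 visit held before dosing resumes can supply it. After a Day 21 draw the earliest date is 21 + 8 = 29, the planned restart day. In Cycle 2 it falls on Day 50 or later, when no dosing decision remains. The text should also say whether a normal first repeat ends the sequence, because Table 2 stops binders in the off week once phosphorus is normal.

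Moving the draw earlier than Day 14 would leave room for an on-drug test 8 days later, but it would see less exposure while the drug accumulates (ratio 3 to 8 on Days 15 and 28, section 2.4.1). Keeping Day 14 and adding the repeats avoids that trade-off.

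Cost: a footnote, one added rule, and one extra phosphate draw per patient (none if per cycle was already intended), plus triggered repeats. Section 7.4 allows these at a local laboratory.

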5.2.5. Dose Modifications for Infigratinib

Each subject will be allowed a maximum of 2 dose reductions as noted in Table 2. Subjects should discontinue infigratinib if toxicity persists as per criteria in Table 3. Subject management will be based upon investigator evaluations.

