Gra de 3 (ANC < $1.0 - 0.5 \times 10^9/L$)	
Hold dose of infigratinib until resolved to CTCAE Grade \leq 1 or baseline, then
 
 • If resolved within \leq 7 days, maintain dose level of infigratinib • If resolved between > 7 days and 14 days, \downarrow 1 dose level of infigratinib • If not resolved within \leq 14 days, discontinue subject from study drug
Gra de 4 (ANC < $0.5 \times 10^9/L$)	
Hold dose of infigratinib until resolved to CTCAE \leq Gra de 1, \downarrow 1 dose level of infigra tinib
 
 • If not resolved within \leq 14 days, discontinue subject from study drug
Febrile Neutropenia	
Gra de 3 (ANC < $1.0 \times 10^9/L$, single temperature of > $38.3^{\circ}C$ or a sustained temperature of $\geq 38.0^{\circ}C$)	
Hold dose of infigratinib until resolved to CTCAE Grade \leq 1, then
 
 • If resolved within \leq 7 days, \downarrow 1 dose level of infigratinib. • If not resolved within 7 days, discontinue subject from study drug
Gra de 4	Discontinue subject from study drug
Anemia	
Gra de 3 (hemoglobin < 8.0 g/dL)	Hold dose of infigratinib until resolved or corrected to CTCAE Grade \leq 1 or baseline, then maintain dose level
Gra de 4	Hold dose of infigratinib until resolved or corrected to CTCAE Grade \leq 1 or baseline, then \downarrow 1 dose level
Platelet Count Decreased (Thrombocytopenia)	
Grade 3 (platelet < $50 - 25 \times 10^9/L$) without \geq Gra de 2 bleeding	
Hold dose of infigratinib until resolved to CTCAE Grade \leq 1 or baseline
 
 • If resolved within \leq 7 days, maintain dose level of infigratinib • If resolved between > 7 days and 14 days, \downarrow 1 dose level of infigratinib • If not resolved within \leq 14 days, discontinue subject from study drug
Grade 3 (platelet < $50 - 25 \times 10^9/L$) with bleeding or Grade 4 (platelet < $25 \times 10^9/L$)	
Hold dose of infigratinib until resolved to CTCAE Grade \leq 1 or baseline, then \downarrow 1 dose level
 
 • If not resolved within \leq 14 days, discontinue subject from study drug

Worst Toxicity CTCAE (v5.0) Grade (Unless Otherwise Specified)	Recommended Dose Modifications any Time During a Cycle of Therapy
INVESTIGATIONS – RENAL	
Serum Creatinine	

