Grade 2 central serous retinopathy and central serous retinopathy-like events	Hold infiratinib until resolved to \leq Grade 1 and continue ophthalmologic evaluation 
 If resolved within \leq 14 days, \downarrow infiratinib by 1 dose level If resolved after $>$ 14 days, discontinue infiratinib
Gra de 3 central serous retinopathy and central serous retinopathy-like events and any other Grade 3 eye disorders	Hold infiratinib until resolved to Gra de \leq 1 
 If resolved within \leq 14 days, \downarrow infiratinib by 1 dose level If resolved after $>$ 14 days, discontinue infiratinib
Grade \geq 1 retinal vein occlusion, Grade 4 central serous retinopathy and central serous retinopathy-like events, and Grade 4 other eye disorders	Discontinue subject from study drug
Other Ocular/Visual Toxicity	

Worst Toxicity CTCAE (v5.0) Grade (Unless Otherwise Specified)	Recommended Dose Modifications any Time During a Cycle of Therapy
Gra de \geq 3	
Hold infigra tinib until resolution to \leq Gra de 1
 
 • If resolution within \leq 14 days, \downarrow 1 dose level • If resolved after $>$ 14 days, discontinue infigritinib
GENERAL DISORDERS	
Fatigue	
Gra de \geq 3	
Hold dose of infigritinib until resolved to CTCAE Grade \leq 1
 
 • If resolved within \leq 7 days, maintain dose level of infigritinib. • If resolved after $>$ 7 days, discontinue subject from study drug
SKIN AND SUBCUTANEOUS TISSUE DISORDERS	
Alopecia	
Gra de 1	
Continue infigritinib
 
 • Minoxidil 5% (OTC) solution or foam once daily to scalp
Gra de 2	
Continue infigritinib
 
 • Minoxidil 5% (OTC) solution or foam twice daily to scalp • Fluocinonide 0.05% solution daily to scalp
Palmar-plantar erythrodysesthesia syndrome	
Gra de 0/1	
Continue infigritinib
 
 • Urea 20% or ammonium lactate 12% lotions bid to hands and feet
Gra de 2	
Continue infigritinib
 
 • Urea 20% or ammonium lactate 12% bid to hands and feet • Fluocinonide 0.05% cream bid to hands and feet
Gra de 3	
Hold infigra tinib until resolved to Gra de \leq 1
 
 • Urea 20% or ammonium lactate 12% bid to hands and feet • Fluocinonide 0.05% cream bid to hands and feet
Paronychia	

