Gra de 1	
Continue infigritinib
 
 • Clindamycin 1% solution around and under nails tid • Soak for 15 minutes daily in white vinegar in tap water 1:1
Gra de 2	
Continue infigritinib
 
 • Cefadroxil 500mg bid or TMP/SMX DS bid for 14 days • Soak for 15 minutes daily in white vinegar in tap water 1:1 • Obtain bacterial cultures to confirm sensitivity to antimicrobial • Dermatology consultation

Worst Toxicity CTCAE (v5.0) Grade (Unless Otherwise Specified)	Recommended Dose Modifications any Time During a Cycle of Therapy
Gra de 3	
Hold infigra tinib until resolved to Gra de ≤ 1
 
 • Cefadroxil 500mg bid or TMP/SMX DS bid for 14 days • Obtain bacterial cultures to confirm sensitivity to antimicrobial • Dermatology consultation
Stomatitis	
Gra de 1	
Continue infigritinib
 
 • Dexamethasone elixir 0.5mg/mL swish and spit 1 teaspoon (5mL) tid.
Gra de 2	
Continue infigritinib
 
 • Dexamethasone elixir 0.5mg/mL swish and spit 1 teaspoon (5mL) tid.
Gra de 3	
Hold infigra tinib until resolved to Gra de ≤ 1
 
 • Dexamethasone elixir 0.5 mg/mL swish and spit 1 teaspoon (5 mL0 tid • Clotrimazole 10 mg lozenges qid
OTHER CLINICALLY SIGNIFICANT AEs	
Gra de 3	
Hold dose of infigritinib until resolved to CTCAE Grade ≤ 1, then \downarrow 1 dose level of infigra tinib
 
 • If not resolved within ≤ 14 days, discontinue subject from study drug
Gra de 4	Discontinue subject from study drug

Abbreviations: AE, adverse event; ALT, alanine aminotransferase; ANC, absolute neutrophil count; AST, aspartate aminotransferase; CT, computed tomography; CTCAE, Common Terminology Criteria for Adverse Events; ECG, electrocardiogram; QTcF, QTc corrected by Fridericia's formula; ULN, upper limit of normal.

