8.2.7. Ophthalmic Assessments

Ophthalmologic examination will be performed by an ophthalmologist, or optometrist who is supervised by an ophthalmologist, at the times indicated in [Section 1](#). These assessments will include visual acuity testing, slit lamp examination of the anterior eye segment, intraocular pressure, and fundoscopy. Additional examinations such as specular microscopy (that enables a magnified, direct view of the corneal epithelium), corneal pachymetry, retinal optical coherence tomography (OCT), and dilated fundoscopy will be performed as clinically indicated.

9. STATISTICAL PLAN:

The primary objective is to evaluate the safety and tolerability of infigratinib as neoadjuvant therapy. Up to 20 patients will be enrolled in the study. The study will estimate proportion of patients who are not able to complete treatment (discontinuation) due to excessive toxicity along with the 90% exact confidence interval (NOTE: excessive toxicity is defined as treatment related adverse events that cause patients not to complete 2-cycles of planned treatment schedule). Toxicities will be tabulated using frequency and percentage by grade and their relations to treatment. Assuming a 30% of discontinuation due to excessive toxicity, the 90% confidence interval would be (13.1%, 46.9%) with a sample size of 20. Toxicity data will be summarized for the whole group of patients and for patients with eGFR \geq 50 and eGFR 30-49 separately. The safety analysis included all patients who received at least one dose of infigratinib.

Toxicity monitoring:

The study will monitor the incidence of not completing treatment or delay >14 days of surgery due to excessive toxicity using this monitoring rule. That is stop the trial early if $\text{Prob}(\text{Ptox} > 0.3 | \text{data}) > 0.85$. Where Ptox denotes the proportion of patients not being able to complete treatment or delay >14 days of surgery. The corresponding stopping boundaries are that the trial will be stopped early if at any time it is observed that $(n \text{ of patients not completing treatment or delay } >14 \text{ days of surgery due to excessive toxicity} / N \text{ of patients treated}) \geq 3/5, 4/(6-8), 5/(9-10), 6/(11-13), 7/(14-16), \text{ and } 8/(17-19)$. This stopping rule will be applied for each cohort of eGFR \geq 50 and eGFR 30-49 separately. If one cohort stops early due to excessive toxicity, the other will continue accruing as per protocol criteria and toxicity monitoring rule.

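### Table 2 gives a Grade 4 non-retinal eye event two different actions, stop for good or hold and restart, with no rule for choosing between them

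*Combined protocol and SAP*

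**What the plan says.** The eye section of Table 2 has two blocks.

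- **Retinal Disorders.** The Grade 3 row covers central serous retinopathy and then adds "and any other Grade 3 eye disorders". Its action is to hold, reduce one level if resolved within 14 days, and discontinue if resolution takes longer. The last row of the block includes "Grade 4 central serous retinopathy and central serous retinopathy-like events, and Grade 4 other eye disorders", and its action is to discontinue.
- **Other Ocular/Visual Toxicity.** There is one row, for Grade 3 or higher. The action begins "Hold infigra tinib until resolution to" Grade 1 or lower. Resolution within 14 days leads to a restart one level lower, and later resolution leads to discontinuation.

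The table ends with a general row, "OTHER CLINICALLY SIGNIFICANT AEs", under which Grade 4 means discontinuation. Section 5.2.5 adds: "Subject management will be based upon investigator evaluations".

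**The concern.** Two investigators who each follow Table 2 correctly could treat the same patient in opposite ways: one ends infigratinib permanently, the other restarts it at 100 mg after a 125 mg start. The conflict concerns the most severe eye events that a patient can survive, so the rule should leave no doubt.

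Eye toxicity is an expected effect of this drug. Section 2.4.2 reports eye-related adverse events in 44.7% of phase 1 patients, judged treatment-related in 33.7%. It also describes a serious keratitis that led to discontinuation. What is at stake is mainly the safety of re-exposing a patient after a Grade 4 eye event.

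**Working it through.** No figure in the plan needs reproducing here; the check compares rows.

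**Step 1. Which rows does a non-retinal eye event meet?** The inputs are the two eye blocks of Table 2, read literally.

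| Grade | Time to Grade 1 or lower | Retinal block | Other Ocular row | Same final action? |
|---|---|---|---|---|
| 1 or 2 | any | no match | no match | no rule, no conflict |
| 3 | within 14 days | hold, then one level lower | hold, then one level lower | yes |
| 3 | over 14 days | hold, then discontinue | hold, then discontinue | yes |
| 4 | within 14 days | discontinue at once | hold, then one level lower | **no** |
| 4 | over 14 days | discontinue at once | hold, then discontinue | yes, off drug |

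Only one line conflicts. A retinal Grade 4 event is not affected, because the second block covers ocular events other than retinal ones.

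**Step 2. Does any other text break the tie?**

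- The opening text of section 5.2.5.1 refers the reader back to Table 2 for the restart dose.
- Section 5.2.5 leaves management to the investigator, which permits either action but does not say which row was meant.
- Section 5.2.5.2 provides for specialist consultation without ranking the rows.
- Section 6.1.1 lists adverse events only as a possible reason to stop.

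None of these is a precedence rule.

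**Step 3. Does the rest of Table 2 show the intent?** The Grade 4 actions elsewhere are:

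- *Clinical toxicities that discontinue:* QTcF prolongation with serious arrhythmia, other cardiac disorders, febrile neutropenia, neurotoxicity, pancreatitis, diarrhea, uncontrolled vomiting, and the general row.
- *Clinical exception:* fatigue of Grade 3 or higher, which may restart if it resolves within 7 days.
- *Laboratory findings that allow resumption:* neutropenia, low platelets, anemia ("Hold dose of infigratinib until resolved or corrected to CTCAE Grade" 1 or baseline, then one level lower), and raised pancreatic enzymes ("For any Grade 4 a symptomatic lipase or a mylase elevation, drug should be held", with continuation discussed with the medical monitor).

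The rows that allow resumption are laboratory findings, apart from fatigue. A Grade 4 eye event is a clinical toxicity, so the pattern favours discontinuation.

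**Step 4. How often could this arise?** Section 2.4.2 gives eye events overall without a breakdown by grade. The one serious eye event it describes is Grade 2. Section 2.4.1 mentions a Grade 1 corneal toxicity at 150 mg. No Grade 4 eye event is reported, but without a grade distribution this is not a documented count of zero. A rate cannot be derived.

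**The case against.** The best defence is the subheading. The discontinue row sits under Retinal Disorders, so its other eye disorders may mean other retinal disorders. On that reading every row has its own purpose, the second block no longer duplicates the first at Grade 3, and the conflict disappears. This is plausible. But the table does not state the limit, and the words used match the parent heading for all eye disorders. The reading would also make a Grade 4 corneal event eligible for restart while the general row stops the drug for other Grade 4 events. If the sponsor means this, the table should say so.

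A second defence is that the actions are recommendations, that eye disorders are confirmed by ophthalmologic examination, and that the investigator decides. This lowers the risk of a bad decision but does not remove the contradictory guidance.

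A reader might go further and infer that the overlap distorts the primary endpoint, since section 9 counts "treatment related adverse events that cause patients not to complete 2-cycles of planned treatment schedule". The documents do not support this as a measurable effect. They give no Grade 4 eye-event rate. They do not say how held doses count toward completing two cycles. They also leave room for the schedule to move: Cycle 2 is at day 29 ± 7, the pre-operative visit at day 57 ± 14, and section 9 monitors surgery delays of more than 14 days. Any figure would rest on assumptions about onset, recovery and schedule that the protocol does not supply.

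**Conclusion.** The inconsistency is real and narrow. Read literally, Table 2 assigns both discontinuation and hold-and-restart to a Grade 4 non-retinal eye event. The outcome differs only when such an event falls to Grade 1 or lower within 14 days.

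It would be too strong to say that Table 2 gives no hint of the intended action: the general row and most Grade 4 clinical rows point to stopping. That pattern is indirect evidence, however, and an investigator at the bedside should not have to infer it.

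The size is one grade of one class of event, with no such case reported in the documents and no rate from which to project one. The point stands as a patient-safety clarification and not as a threat to the primary analysis. It assumes that other eye disorders carries its ordinary meaning and is not silently limited to the retina.

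**What to change.** In the Other Ocular/Visual Toxicity block of Table 2, change the trigger from Grade 3 or higher to Grade 3. Grade 4 eye events then always lead to discontinuation, and the Grade 3 action is unchanged.

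The sponsor's clinicians should confirm this before the edit. If they want restart to be possible after a non-retinal Grade 4 event, the alternative is to remove the reference to Grade 4 other eye disorders from the discontinue row, so that only one instruction remains.

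Either way the cost is one cell of one table, with no added visit, form field or patient.
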